- **Agitation:** Agitation will be measured via RASS (Richmond Agitation Sedation Scale) score¹ assessed by research staff every 60 minutes during the four 4-hour periods (Days 1 and 2) when subjects are using novel and traditional restraints, and then every 4 hours during Days 3-6 when subjects are using their randomly assigned device. RASS is a validated and reliable ordinal measure of sedation/agitation status in the ICU ranging from -5 to +4.¹ All study personnel will be trained in measuring RASS score. We hypothesize that *Exersides™* will reduce **delirium, agitation, and use of sedatives**, analgesics and antipsychotics.
- **Delirium:** Delirium will be measured via CAM-ICU (Confusion Assessment Method for the ICU) at its maximum appropriate frequency of every 4-hours during Days 1-2, and then every 12 hours during Days 3-6. The CAM-ICU score is a validated and reliable binary measure of delirium status in the ICU.¹ All personnel will be trained in measuring CAM-ICU. Our group has extensive experience with CAM-ICU.¹
- **Sedative, analgesic, and antipsychotic medication use:** Throughout the 6-day study period, use and dose of medications will be assessed by chart review. Medications in these categories include, but are not limited to, opiates, benzodiazepines, typical and atypical antipsychotics, propofol, and dexmedetomidine.

Outcome 3: Satisfaction with and acceptability/perceptions of the device

Satisfaction and acceptability will be assessed by the Quebec User Evaluation of Satisfaction with Assistive Technology (QUEST 2.0) survey and by semi-structured interviews. We hypothesize that *Exersides™* will demonstrate high satisfaction, assessed both quantitatively and qualitatively, among ICU clinicians, families and patients.

- **Satisfaction:** The QUEST 2.0 is a valid, reliable, and widely used 12-question survey assessing satisfaction with technological devices.¹ It is scored from 1-5, with >3.26 considered high satisfaction. The QUEST 2.0 has 2 subscales (satisfaction with device and with services). Satisfaction with the *Exersides™* restraint will be assessed using the device subscale, which has good test-retest stability (ICC 0.82).¹⁷

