During the first 2 Days, the primary endpoint (activity) is measured for each period on each day, such that each patient will contribute 4 longitudinal measurements. This primary endpoint is measured as total activity, the sum of the recorded activity counts for the corresponding period/day. Secondary endpoints include agitation (normal vs. sedated/agitated as defined by RASS), delirium (positive vs. negative for delirium based on CAM-ICU, among patients who are not comatose [RASS -4, -5]) and medication use (quantified by computing the total dose of medications received within each class (Outcome 2) using standard equivalency conversions for drugs within each class, as done in our prior research.¹ Analysis will include summary statistics (mean, median, standard deviation and quantiles) of the key co-interventions (see Aim 3I above) and the RCT endpoints (Table 8), separately for each period over the 2 days, stratified by treatment group.

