To estimate the effect of the novel restraint, a linear model will be fit for the Log(total activity) as a function of main terms for treatment (Group A vs. B), time period (1pm-5pm vs. 9am-1pm), and treatment order (BA/AB vs. AB/BA). The natural logarithm is applied to the primary endpoint to reduce right skew in the distribution of total activity, with the exponentiated regression coefficient for the main term for treatment (A vs. B) in the linear regression model representing the relative difference in median total activity comparing the novel vs. traditional restraint, which will quantify the treatment effect. The linear model will be fit using weighted least squares to account for the correlation in the primary endpoint within a patient over time; the correlation structure will be specified as unstructured and allow for the possibility that the variance of the primary endpoint may be different in each period/day. The same linear models will be applied to the continuous secondary endpoints (e.g. medication dose). For the binary secondary endpoints, the effect of the novel vs. traditional restraint will be quantified using a longitudinal logistic regression model as a function of the same covariates (treatment, period, and treatment order). The longitudinal logistic regression model will be fit using generalized estimating equations allowing for an unstructured within-patient correlation structure. Activity, agitation, delirium and medication use will continue to be measured up to ICU discharge, death or Day 6. Starting on Day 3, the endpoints will be expressed as every 4-hour total activity counts, agitation assessment and total medication use, as well as every 12-hour delirium. With the data starting on Day 3, we will explore the long-term effects of the restraints by fitting linear and logistic longitudinal regression models that include main terms for treatment and time and the interaction of treatment and time. Time will be modeled as a restricted cubic spline with degrees of freedom selected by model fit statistics. As secondary outcomes are hypothesis-generating, we will not correct for multiple comparisons, but will consider the number of comparisons when interpreting results.

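### The exploratory Day 3-6 models omit site and the baseline outcome values, which costs precision (power, for binary outcomes); their correlation structure should also be named

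*Combined protocol and SAP*

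**What the plan says.** **Days 3-6.** Statistical Analysis Plan a) explores longer-term effects by "fitting linear and logistic longitudinal regression models that include main terms for treatment and time and the interaction of treatment and time", with time as a restricted cubic spline. The unit is given: "Starting on Day 3, the endpoints will be expressed as every 4-hour total activity counts, agitation assessment and total medication use", with delirium every 12 hours. No further covariate, correlation structure or standard error is named for these models.

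**What is available for adjustment.** Under Randomization, allocation is 1:1 in small blocks within site. Table 7 lists a baseline assessment for RASS, CAM-ICU and medication. For actigraphy it lists only continuous recording during the study.

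**Other adjustment in the plan.** The same SAP section adds time-varying factors such as organ failure as a sensitivity analysis, and sex with its treatment interaction. Inclusion of Women and Minorities allows sex and race/ethnicity as covariates if needed. None of these brings in site or the baseline outcome.

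**Days 1-2.** For the linear model of the primary endpoint, with four values per patient, "the correlation structure will be specified as unstructured". Binary endpoints use "generalized estimating equations allowing for an unstructured within-patient correlation structure", with treatment, period and order as covariates. Agitation is a two-category RASS state, and RASS is scored hourly in the four periods (16 scores). The SAP does not say whether each score or one value per period is analysed. Summaries are to be given "separately for each period over the 2 days, stratified by treatment group".

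**The concern.** On Days 1-2 each patient is their own control, so stable differences between patients drop out of the device comparison. From Day 3 they do not. Each patient wears one device, and differences between patients become the main noise in a comparison of two small arms. A baseline value of the same outcome is the obvious means of removing part of that noise, and it is already collected. The study-design text justifies the Day 3-6 stage on the ground that agitation, delirium and medication use are better judged over days than hours. Avoidable imprecision therefore falls where these outcomes matter most: a real effect is easier to miss and intervals are wider.

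The second matter is the unnamed correlation structure. If it is left open, it will be chosen after the data are seen. If the analyst copies the unstructured form from Days 1-2, the number of correlations could exceed what 54 patients can support.

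**Working it through.** **Inputs from the documents.** N = 54, 1:1, so 54/2 = 27 per arm at most; two-sided 5% (SAP a); 80% power (Sample size). Days 3-6: 6 × 4 = 24 four-hourly values, or 2 × 4 = 8 delirium values.

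**Assumed, because the documents give none for these outcomes.** The correlation r between baseline and a patient's Day 3-6 mean, prevalences, between-patient SDs, odds ratios and the rate of early leaving. The plan gives no power figure for Days 3-6, so there is none to reproduce. Its 56% detectable increase concerns Days 1-2 activity and has no bearing here.

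**1. Continuous outcomes.** Adjustment multiplies the variance of the treatment effect by about 1 − r². The detectable difference, in SDs of the patient mean, is (1.9600 + 0.8416) × √[(2/n)(1 − r²)], with n per arm. The column for 20 per arm illustrates fewer patients continuing.

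| r | 1 − r² | n = 27 | n = 20 |
|---|---|---|---|
| 0 (unadjusted) | 1.00 | 0.762 | 0.886 |
| 0.3 | 0.91 | 0.727 | 0.845 |
| 0.5 | 0.75 | 0.660 | 0.767 |
| 0.7 | 0.51 | 0.545 | 0.633 |

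The formula ignores the cost of estimating the extra terms. A simulated check gave SE ratios of about 0.97, 0.88 and 0.74, against √(1 − r²) = 0.954, 0.866 and 0.714, with type I error near 5%. Site alone does little: if it explains 1% to 10% of the variance, the SE ratio is √0.99 = 0.995 to √0.90 = 0.949.

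**2. Binary outcomes.** Simulated agitation with the planned spline and interaction, exchangeable GEE, Mancl-DeRouen variance, average device effect, half the patients leaving early, 1,000 replicates:

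| r (about) | Odds ratio | Power, planned terms | Power, plus site and baseline |
|---|---|---|---|
| 0.5 | 0.5 | 25% | 33% |
| 0.5 | 0.3 | 68% | 77% |
| 0.66 | 0.5 | 12% | 17% |
| 0.66 | 0.3 | 27% | 45% |

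Compare within rows only, because unadjusted power already differs between the settings. Type I error was 2.9-3.8% with or without adjustment. The gain is not a smaller SE. In a separate simulation the SD of the log odds ratio went from 0.334 to 0.333 while its mean went from −0.840 to −0.936, and power rose from 69% to 83%. The adjusted model estimates a conditional odds ratio, which lies further from 1.

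**3. Correlations in an unstructured matrix, m(m − 1)/2.** 4 values: 6. 8 values: 28. 16 values: 120. 24 values: 276.

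**4. If unstructured were carried over to 24 values without a small-sample correction** (no true effect, nominal 5%):

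- Binary, average effect, complete or nearly complete data: 14.1-18.1%. A second simulation with a different correlation model gave 20.4-21.1% of completed fits.
- Continuous, average effect, generalised least squares on complete data: 25.1% in one run and 26-28% in another.
- Binary, half leaving early: 96-100% of fits failed.
- Binary, exchangeable with Mancl-DeRouen variance: 3.6-5.0% for the average effect.

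**5. Days 1-2 agitation.** Unstructured GEE on four period values rejected in 5.5-6.9% (5.0-5.5% with Mancl-DeRouen), which is acceptable. On 16 hourly scores it rejected in 13-17% of completed fits.

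**The case against.** **The covariates are optional.** The planned Day 3-6 terms do not bias the test. The gain depends on r, and the study-design text itself stresses how quickly these patients change. At r = 0.3 the detectable difference moves only from 0.762 to 0.727 SD. Site contributes little, and for logistic models the gain is in power for a different estimand. All of this stands, and it is why the point is an improvement and not a correction.

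**A reader might infer that the plan commits to an unstructured matrix on 16 hourly or 24 four-hourly values, and so to inflated false-positive rates.** The documents do not support that. The unstructured GEE is specified for the Days 1-2 binary endpoints. There the period covariate, the absence of an hour term and the per-period summaries all lean to four values. The Day 3 models are introduced separately, with different terms and no structure. What the documents show is missing detail.

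**A reader might also infer that an unstructured fit would nearly always fail, or that the structure itself causes the inflation.** Neither holds in general. On 24 complete binary values, failures ranged from 0 in 150 runs in one package, through 14.5-66%, to 99-100% in other implementations. For continuous outcomes, keeping unstructured but applying an exact small-sample correction brought rejection back to 4.4%. Inflation also arises mainly when few leave early, whereas with many leaving early the fit breaks down visibly.

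**Scope.** Day 3-6 delirium has at most 8 values. Medication has 4 if analysed daily, as Table 7 suggests. The secondary outcomes are declared hypothesis-generating.

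**Conclusion.** The point holds as a missed gain in precision. For continuous Day 3-6 outcomes the variance could be cut by about 9%, 25% or 49% at assumed r of 0.3, 0.5 or 0.7, nearly all of it from baseline. For binary agitation, power rose by 5 to 18 percentage points in the settings tried. The size rests on assumed correlations, prevalences and effects; the direction does not depend on any one of them.

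Adjustment should not be taken to repair selection. Whether a patient still needs restraints on Day 3 is settled after randomisation, and baseline covariates do not restore the comparison if the devices influence it.

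The correlation structure is a secondary, conditional point: about 14-28% null rejection for the average effect only if unstructured is carried over to 24 values uncorrected, or frequent failure to fit when patients leave early. The Days 1-2 agitation unit is a clarification, not an error. The primary analysis is unaffected.

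**What to change.** Amend Statistical Analysis Plan a) as follows.

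1. In the Day 3-6 models, add site and the last pre-randomisation value of the same outcome for agitation, delirium and medication. Table 7 says only baseline, so state that it precedes randomisation. Code baseline RASS in the same two categories as the outcome, since both ends of the scale count as abnormal. For activity add site only: no baseline actigraphy is listed, and Days 1-2 recordings come after randomisation.
2. Report adjusted odds ratios as conditional on site and baseline.
3. For the four-hourly endpoints, name an exchangeable working correlation with a small-sample-corrected sandwich variance (for example Mancl-DeRouen with a t reference). Name the treatment test, for example the effect averaged over Days 3-6.
4. State which randomised patients enter the Day 3-6 analysis, and reconcile daily (Table 7) with four-hourly (SAP) medication values.
5. Confirm that Days 1-2 agitation is one binary value per 4-hour period, with the rule that forms it, and keep the unstructured GEE there. If hourly scores are intended, use the approach in item 3.

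The cost is SAP wording. Site and the baseline values are already collected, and with three sites the models gain about three parameters.

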- **Study Sites:** We will recruit patients from 3 hospitals: UVM, JHU and UCLA. These sites were selected due to successful prior collaborations, experience in ICU RCT recruitment, similar sedation practice (Prelim Data 6), experience in ICU mobility/actigraphy, and similar “usual care” (Prelim Data 6). A study overview is in Figure 3.

- **Data Coordinating:** Data coordination will occur through integrated efforts between Healthy Design and all 3 study sites, with full support for design, conduct, monitoring, and analysis. An employed data coordinator will create a study database in RedCAP

and will manage data from all 3 enrolling sites. Data coordination, cleaning, and subsequent analyses will be overseen by Drs. [name] (PhD biostatistics faculty/ co-I) with Drs. [name], [name], and [name]. [name] will oversee RCT conduct, including regulatory/ NIH reports. And employed study monitor will conduct site monitoring visits during the RCT.

- **Study Leadership of RCT:** To address leadership and communication issues, an Executive Committee (“EC”: Drs. [name], [name], and [name], along with [name] [Project Manager, UVM]) will meet twice monthly by phone to discuss RCT conduct. For issues that require broader input, the RCT also will have a Steering Committee that includes the EC plus Drs. [name] (UCLA site PI), [name] (Biostatistician), [name] (Nurse co-investigator), [name] (aging/delirium co-investigator) that will meet monthly or as needed. Each site-PI will supervise daily operations, along with site research staff supported by per-patient capitation payments. All investigators will co-author publications, with author order mutually agreed upon in advance.
- **Patients (n=54):** Eligibility criteria are identical to the cohort study in Aim 2 (Table 5).
- **Consent:** As in the study in Aim 2 (STTR Phase I), consent will most often occur via LARs with participant re-consent upon regaining capacity. See below under section on Consent.
- **Randomization:** After consent, patients will be randomized (1:1) to Group A vs B (Fig. 4) via UVM’s web-based system (24 hrs/day), with variable-sized blocks of 2 or 4, stratified by site.

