- **Blinding:** Due to the nature of restraint devices, we cannot blind patients, families, or ICU clinicians. To minimize bias, the primary outcome (actigraphy) will be analyzed by an outcome assessor blinded to patient identity or study group ([name]) and key co-interventions will be standardized with planned analyses to evaluate balance between groups (see Statistical Analysis Plan).
- **Standard ICU co-interventions for all patients:** Important aspects of routine care will be standardized for BOTH study groups based on existing protocols at all sites, including: 1) turning by RN every 2 hr while in bed; 2) sedation/delirium management as per published practice guidelines (see Preliminary Data #6); 3) daily spontaneous breathing trials and ventilator weaning protocols, and 4) nutrition as per registered dietician consultation. These co-interventions are recorded electronically to easily facilitate the study monitoring plan.
- **On-study data collection:** Demographic, laboratory, physiological, and rehabilitation data will be collected (see Tables 5 and 6).

Table 5: Patient Variables -- Collected at Enrollment

Patient Variables – collected at enrollment/baseline	Collection Method	Measurement Scale
Demographic data (e.g. age, sex, race, marital status)	Chart review	Continuous/Binary/Categorical
Height & weight; body mass index	Chart review	Continuous
Comorbidities: Charlson ^a & Functional Indices ^b	Chart review	Ordinal
Baseline function: Katz Activities of Daily Living, ¹¹ and Clinical Frailty Scale ¹²	Proxy interview (see Outcomes below)	Continuous/Ordinal
ICU admission diagnosis (e.g. sepsis, renal failure)	Chart review	Categorical
Severity of illness: APACHE II ^d	Chart review	Continuous
Alzheimer’s disease and related dementia: IQCODE-SF survey ^e ; Delirium Risk Score	Chart review;	Categorical

^aCharlson Index: a score for in-patients derived from 19 comorbidities; an increased score reflecting increased 1-year mortality.¹³

^bFunctional Comorbidity Index: an 18-diagnosis scale for ICU patients predicting 1-year SF-36 physical function.¹

^dAPACHE II: Severity index using age, medical conditions, & acute physiology. Scores reflect increased short-term mortality.¹⁴

^eIQCODE-SF (Short Form of Informant Questionnaire of Cognitive Decline in the Elderly) is a validated proxy-based measure of baseline cognitive impairment commonly used in studies of hospitalized and critically ill patients¹

[figure not shown]

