- **Sample size:** Sample size was determined for the primary outcome, arm activity, as assessed by actigraphy over Days 1 and 2 (defined as total activity counts per 4-hour period: 9am-1pm and 1pm-5pm). Although Phase II is 24 months long, there are only 18 months for recruitment, as we need 3 months for startup and 3 months for close out (Table 10). Across the 3 study sites, we expect to recruit 1 patient per site per month during the 18-months, yielding a total N=54. Experience enrolling ICU patients in RCTs at each site.¹ suggests that 1 patient/month/site is feasible and mirrors empirical data, with our analysis of 33,106 patients from 23 RCTs, demonstrating median (IQR) enrollment of 0.90 (0.50–1.79) patients/month per site.²⁰

Assuming N=54, we calculated the treatment effect (i.e. the relative change in the median total activity) that can be detected with 80% power and 5% Type I error rate. We used the following assumptions (these data were informed by our preliminary data with modest adjustments for expected differences for the proposed 3-center study): (1) 9am-1pm median total activity = 3000, (2) 1pm-5pm median total activity = 2700, (3) variance of Log(total activity) set conservatively to 2.5 and 6.0 for 9am-1pm and 1pm-5pm periods, respectively, (4) Log(total activity) has 0.85 correlation within a patient over time, and (5) no cross-over effect of the restraints. Using N=10,000 simulation, the 54-patient sample size can

detect a 56% relative increase in median total activity comparing the novel vs. traditional restraint (median of 3000 vs. 4674).

- **Statistical Analysis Plan**

a) Summary for all Aims: All analyses **will follow the intention-to-treat (ITT) principle**. A 2-tailed p-value <0.05 will be statistically significant. As described in the Study Design (Section 3K), the within-patient crossover design removes patient-specific effects from evaluation of the treatment effect. Potential pitfalls of this design include order effects, carryover effects, and patient dropout. To avoid order effects, we randomize whether patients start the trial with the novel vs. traditional restraint (Figure 4). Carryover effects (i.e. one part of the study affecting subsequent parts) and drop out considerations are discussed further below.

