Subgroup analysis will be performed in eligible patients with baseline history of Alzheimer's disease and related dementia. To evaluate the potential effect of time-varying patient factors (not strictly controlled via a within-patient crossover design – e.g. organ failure status (Table 7)) on the primary results, sensitivity analysis of the above regression results will be conducted by including such variables into regression models. **To evaluate for any sex-specific effect in this study, sex will be included in the regression model as a co-variate and as a statistical interaction term with the main term for treatment (A vs. B) to fully address NIH requirements.**

b) Minimizing missing data: Our primary outcome is assessed during the first 2 study days when missing data are uncommon in our prior studies.¹ Missing data will be minimized through ongoing contact with participants/families and ICU nurses to increase likelihood of obtaining data. Missing data will be described for all variables, and patient characteristics will be compared between those with vs. without missing outcomes.¹ Based on our preliminary data and experience with other studies using similar eligibility criteria, we expect <5-10% missing data due to death or other patient loss, and any missing will not be associated with treatment allocation; thus, no imputation will be performed and we would enroll up to 60 total patients, if needed, to compensate for missing data to obtain the primary outcome on N=54 patients.

c) Data safety monitoring board (DSMB) meetings: The DSMB (see Data Safety document) will meet before the RCT (in STTR Phase II) begins, and after half of the patients have been enrolled into the RCT to review safety and recruitment data only. As this is a small RCT, there will be neither interim analyses to evaluate efficacy nor stopping rules for efficacy or futility.

For research involving survey, questionnaires, etc.: Describe the setting and the mode of administering the instrument and the provisions for maintaining privacy and confidentiality. Include the duration, intervals of administration, and overall length of participation. (describe and attach all instruments)

Not applicable

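### The dementia subgroup is analysed only within dementia patients, with no treatment-by-dementia interaction, so it cannot show whether the effect differs; a small-sample test there may also well exceed its nominal 5%

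*Combined protocol and SAP*

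**What the plan says.** Under Statistical Considerations for RCT, the Statistical Analysis Plan gives dementia one sentence: "Subgroup analysis will be performed in eligible patients with baseline history of" Alzheimer's disease and related dementia. It names no model, definition, expected number, power or comparison with the remaining patients. Later in the same paragraph, sex is to enter the regression both as a covariate and as an interaction with treatment.

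The only effect model described for activity on Days 1 and 2 is the primary one. It has main terms for treatment, time period and treatment order, four measurements per patient, and a weighted least squares fit in which "the correlation structure will be specified as unstructured and allow for the possibility that the variance of the primary endpoint may be different" in each period and day. No degrees-of-freedom method or small-sample correction is named. The significance rule for all aims is "A 2-tailed p-value <0.05 will be statistically significant".

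Sample size is 54, and randomization is 1:1 "with variable-sized blocks of 2 or 4, stratified by site", so not by dementia status. Severe pre-existing cognitive impairment is an exclusion. Table 5 (patient variables at enrollment) has a row for Alzheimer's disease and related dementia that lists IQCODE-SF, which according to its footnote "is a validated proxy-based measure of baseline cognitive impairment". The same row lists a Delirium Risk Score, gives chart review as the collection method, and gives the scale as categorical. No rule turns these into a yes/no subgroup.

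**The concern.** There are two separate problems.

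The first needs no assumption. An analysis confined to dementia patients estimates the effect in them and makes no comparison. A significant result there does not show that the effect is larger than elsewhere, and a non-significant one does not show that it is smaller or absent. The plan uses an interaction for sex but not for dementia, although the Background and the Inclusion of Children section tie the project to a dementia funding announcement.

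The second is conditional. If the subset is analysed with the primary model, four mean coefficients and ten variance-covariance parameters (4 x 5 / 2) are estimated from a handful of patients. Standard errors that treat an estimated unstructured covariance as known are too small in such samples, so the test rejects too often. A chance finding in dementia patients could then be reported at a nominal 5% that does not apply.

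**Working it through.** **Inputs.** From the sample size paragraph and the Statistical Analysis Plan: two-sided alpha 0.05; N = 54, taken as 27 per sequence; four measurements per patient; variance of log activity 2.5 (9am-1pm) and 6.0 (1pm-5pm); within-patient correlation 0.85; no carryover; mean model of intercept, treatment, period and order. Assumed, because the documents are silent: 6 to 20 dementia patients, and the estimation method and reference distribution.

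**1. The plan's own figure.** No figure is given for the subgroup. For the whole trial the plan says that 54 patients can "detect a 56% relative increase in median total activity comparing the novel vs. traditional restraint (median of 3000 vs. 4674"), a log ratio of ln(4674/3000) = 0.443. Generalised least squares with the stated inputs and exchangeable correlation gives a standard error (SE) of 0.0990 and a detectable ratio of exp((1.96 + 0.84) x 0.0990) = 1.32. With AR(1) correlation it is 1.33. The 56% is therefore not reproduced. This does not affect step 2, which is computed under no treatment effect. It does bear on power (step 3).

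**2. False-positive rate if the primary model is refitted to the subset alone.** Simulation under no effect with unstructured covariance; 5,000 to 8,000 runs per cell, Monte Carlo error about 0.5 point. Ranges show the spread over repeated simulations.

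| Dementia patients | REML, Wald z | REML, t(4n-4) | REML, t(n-2) | ML, Wald z |
|---|---|---|---|---|
| 6 | 39% | | | 46% |
| 8 | 25% | 23% | 16-17% | 30% |
| 12 | 14-15% | 14% | 10-11% | 17% |
| 16 | 12% | 11% | 9% | 13% |
| 20 | 10% | | | 10% |

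Data generated with AR(1) correlation give 24% at n = 8 and 15% at n = 12 (REML, Wald z). With all 54 patients the rate is 6-7%, so the excess comes from fitting this model to few patients. Kenward-Roger applied to the subset alone reduced it only to 10.7% at n = 8 and 8.4% at n = 12 (a single simulation).

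**3. Interaction in the full model.** With m dementia patients, balanced sequences and known covariance, the SE of the interaction is 0.0990 x sqrt(54/m + 54/(54 - m)).

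- m = 8: 0.0990 x sqrt(6.75 + 1.17) = 0.279. Ratio of effects detectable with 80% power: exp(2.80 x 0.279) = 2.18. Power at a ratio of effects of 1.558: Phi(0.443/0.279 - 1.96) = 36%.
- m = 12: 0.0990 x sqrt(4.50 + 1.29) = 0.238. Detectable ratio of effects 1.95; power 46%.

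Simulating the fitted 54-patient model (3,000 runs) gives power of 37%, 43% and 49% at m = 8, 10 and 12 with a normal reference. The false-positive rate of the interaction test is 6.4-6.9% (normal) or 5.8-6.1% (t, 52 df). With Kenward-Roger it was 5.2% at m = 8 and 4.7% at m = 12 (a single simulation of 2,500 runs each).

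If the plan's 56% is right, its implied SE is 0.443/2.80 = 0.158 rather than 0.0990. The same formula then gives interaction SEs of 0.445 and 0.381, and power of only about 17% and 21% at m = 8 and 12.

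**4. A valid within-subgroup test.** For each patient take (y1 - y2 - y3 + y4)/2, with the sign reversed for the other sequence. This estimates the treatment effect, and main effects of time of day and of day cancel. A one-sample t test on n-1 df rejected a true null in 5.1% of trials at n = 8 and 4.9% at n = 12.

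**The case against.** The strongest reply is that the subgroup sentence names no model, so an error rate computed from the unstructured model belongs to an analysis the plan has not committed to. That is right as far as it goes. Reuse of the primary model is the natural reading because no other model for this endpoint is described, but it is an inference. The text supports only the statement that the subgroup analysis is unspecified and that its likeliest form is anti-conservative in small numbers.

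A reader might infer a fixed false-positive rate of about 25%, or several times the nominal level in all cases. The documents do not support this: they give no dementia prevalence, and weighted least squares fixes neither REML nor a z reference. With 16 patients and t(n-2) the rate is 9%. With 6 patients and a z test it is 39%.

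A reader might also infer that IQCODE-SF plays no part. Table 5 lists it under the dementia variable; what is missing is the rule that turns it, or chart history, into subgroup membership.

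Estimating the effect within the funder's target population is a legitimate aim, and the plan states no hypothesis that the effect differs by dementia status. Nor do the documents show that the subgroup result will be used as a headline claim. That limits the seriousness of the point. It does not make a subset-only result informative about a difference.

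The plan calls its secondary outcomes hypothesis-generating, but it does so to justify no multiplicity correction. That wording neither labels this subgroup analysis exploratory nor excuses a single test that misses its own level.

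**Conclusion.** The point holds in two parts. Without any assumption: the planned dementia analysis makes no comparison with other patients, so it cannot show whether the effect differs by dementia status, and the plan does not say who belongs to the subgroup or how they are analysed.

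Conditionally: if the primary unstructured model is reused without a small-sample correction and about 8 to 12 patients have dementia, the false-positive rate is about 14-25% with a REML Wald z test or 10-17% with t(n-2), against a nominal 5%. Every variant tried between 6 and 20 patients exceeded 5% (about 8% to 46%), so the direction is firm and the size depends on the assumptions.

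It would be wrong to conclude that an interaction test will settle the question. It largely restores the error rate, but with 8 to 12 dementia patients its power is about 37-49% for a ratio of effects of 1.56, and lower if the variability is closer to what the plan's 56% implies. This is not the primary analysis; it is a defect that should be repaired before unblinded data are analysed.

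**What to change.** Amend the subgroup sentence in the Statistical Analysis Plan:

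- **Define the subgroup.** State how IQCODE-SF and chart history in Table 5 determine dementia status at baseline, including any cut-off and which source prevails if they disagree.
- **Test the difference.** Add dementia status and a treatment-by-dementia interaction to the full 54-patient activity model, with a small-sample correction such as Kenward-Roger.
- **Report.** Give the number of dementia patients, both stratum-specific ratios and the ratio of effects with confidence intervals, labelled exploratory. State that a non-significant interaction is not evidence of a common effect.
- **If a within-subgroup test is kept,** use the per-patient contrast with a t test on n-1 degrees of freedom.
- **Optional.** Use the continuous IQCODE-SF score as the modifier, so that all patients contribute. Table 5 lists the scale as categorical, so this is possible only if the raw score is kept.

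The cost is SAP wording, plus retention of the raw score if the optional analysis is wanted; no extra patients or visits are needed. The interaction model assumes the same covariance in patients with and without dementia, and its power remains low. The contrast is somewhat less efficient than the weighted model: with known covariance its standard error at N = 54 is 0.109 against 0.099.
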